11.2 MULTI-INSTITUTIONAL GUIDELINES

11.2.1 IRB Approvals

The PI will provide the NIH Intramural IRB with a copy of the participating institution's initial approval and approved yearly continuing review.

12 HUMAN SUBJECTS PROTECTIONS

12.1 RATIONALE FOR SUBJECT SELECTION

All participants with HCC meeting eligibility criteria may participate in this study. Individuals of any race, ethnic group, or gender will be eligible for this study. Physically impaired persons who otherwise satisfy eligibility criteria will be included in this study.

12.2 PARTICIPATION OF CHILDREN

Children will not be considered as research subjects for this study as ¹⁸F-DCFPyL dosing and toxicity has not been established in this population.

12.3 EVALUATION OF BENEFITS AND RISKS/DISCOMFORTS

12.3.1 Risk/Benefit Assessment

12.3.1.1 Known Potential Risks

12.3.1.2 Risks related to ¹⁸F-DCFPyL

The risks related to ¹⁸F-DCFPyL include radiation exposure allergic reaction, fatigue, dysgeusia, and headache.

12.3.1.3 Risks related to ¹⁸F-FDG

Risks associated with ¹⁸F-FDG include radiation and hypersensitivity reaction.

12.3.1.4 Risks related to IV

The risks associated with IV include temporary pain, bleeding and bruising at the infusion site, leakage of ¹⁸F-DCFPyL and ¹⁸F-FDG into the skin and tissue around the IV and infection.

12.3.1.5 Risks related to PET/CT scan

The risks associated PET/CTs include IV insertion site pain, bruising, dizziness, hypotension, inflammation of the vein or infection at the needle site. Other side effects could include discomfort from lying on a hard surface for an extended period and infection at the IV site or blood.

12.3.1.5.1 Risks of exposure to Ionizing Radiation

This research study involves exposure to radiation from up to 3 ¹⁸F-DCFPyL PET/CTs, 3 regional CTs of a single field-of-view including the liver lesion (for the dynamic portion of the ¹⁸F-DCFPyL PET/CT), up to 3 ¹⁸F-FDG PET/CTs, up to 3 chest/abdomen/pelvis CTs, and 2 CT-guided biopsies. The amount of radiation exposure from these procedures is equal to approximately 12.6 rem. This amount is more than would be expected from everyday background radiation. Being exposed to excess radiation can increase the risk of cancer. The risk of getting cancer from the radiation exposure in this study is 1.3 out of 100 (1.3%) and of getting a fatal cancer is 0.6 out of 100 (0.6%).

Note: dosimetry estimates are based on NIH scanners. Estimates at participating sites may vary.

12.3.1.6 CT contrast risk

Itching, hives, shortness of breath, shock and rarely death are possible risks associated with contrast agents that may be used during CT imaging. Very rarely, the contrast agents used in CT can cause kidney problems for certain participants, such as those with impaired kidney function.

12.3.1.7 MRI and MRI Contrast Risks

Participants are at risk for injury from the MRI magnet if they have metal in their body. There is a possibility that participants may experience claustrophobia. There are risks of back discomfort related to lying in the scanner.

The most common side effects from MRI contrast (gadolinium) include injection site pain, metallic taste, nausea, hives, headaches, difficulty breathing, hypotension and an allergic reaction. Serious but rare side effects such as gadolinium toxicity and nephrogenic systemic fibrosis, or NSF, are most often seen in patients with severe kidney problems.

The risks of an IV catheter include bleeding, infection, or inflammation, pain and swelling of the skin and vein.

12.3.1.8 Risks of Blood Draw

Side effects of blood draws include pain and bruising in the area where the needle was placed, lightheadedness, and rarely, fainting. Up to 17 mL of blood maybe collected at each study visit when a ¹⁸F-DGDPyL PET/CT occurs. Up to 7 mL of blood may be collected at each follow-up visit.

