3.3 STUDY CALENDAR

Procedures	Screening ¹	Baseline ¹ Study Visit 1	Study Visit 2 ¹⁰	Follow-up ¹¹	Disease Progression
Informed consent	X				
Medical Assessment					
Demographics	X				
Medical history	X				
Concomitant medication review	X				
Physical Assessment					
ECOG	X				
Physical exam (including height and weight)	X				
Vital signs	X	X 2	X 2		
Laboratory Assessment					
Hematology (CBC with diff and platelet)	X		X		
Serum chemistry/Acute Care Panel 3	X		X		
Serum or urine pregnancy test 4	X		X		X
Study Intervention					
CT and/or MRI	X 5		X 5		X 12
¹⁸ F-DCFPyL PET/CT imaging 6		X	X		X 12
¹⁸ F-FDG PET/CT imaging 7		X	X		X 12
Adverse Event Monitoring					
Injection site monitoring 8		X	X		X
Adverse event monitoring/Query 8		X	X		X

Procedures	Screening ¹	Baseline ¹ Study Visit 1	Study Visit 2 ¹⁰	Follow-up ¹¹	Disease Progression
Correlative studies					
Tumor marker tests 9, 13		X	X		X
Exome germline control blood collection		X			
Tumor Biopsy		Concurrent with standard of care therapy (pre-treatment or during surgical resection)			
Blood and urine for EVP analysis 13		X	X	X	X
Follow-up evaluations					
Review of clinical chart, phone call or e-mail (or any NIH approved platform)				X	
Collection/review of imaging scans				X	

1. Performed within 30 days prior to administration of ¹⁸F-DCFPyL unless otherwise indicated. Screening procedures such as medical assessment may be performed remotely via any NIH approved platforms.
2. Vital signs will be taken prior to injection of ¹⁸F-DCFPyL.
3. Acute care panel: sodium, potassium, chloride, total CO₂, creatinine, glucose, urea nitrogen, eGFR
4. For female participants of childbearing age (in the absence of prior hysterectomy). Pregnancy tests may be performed as clinically indicated prior to each scan.
5. CT (Chest/Abdomen/Pelvis) and/or MRI (Abdomen) will be performed within 2 months of each ¹⁸F-DCFPyL PET/CT. Imaging may be performed at certified outside facility and provided to study team.
6. Subjects will undergo ¹⁸F-DCFPyL injection and a dynamic PET/CT. Approximately 1 hour (+/- 10 minutes) post ¹⁸F-DCFPyL injection, a static PET/CT imaging performed. Refer to section **3.2.2** for additional information regarding the scanning procedure.
7. ¹⁸F-FDG PET/CT will be performed within approximately 2 weeks before or after each ¹⁸F-DCFPyL scan. Each PET/CT imaging must be approximately a day apart. The order obtained for ¹⁸F-DCFPyL PET/CT and ¹⁸F-FDG PET/CT does not matter.

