8. Event monitoring will be done at the time of injection, and 1 hour post injection. All subjects will be contacted by phone at ~1-3 business days post-injection and will be asked non-leading questions regarding symptoms. At the investigator's discretion, subjects

with safety concerns noted during the post injection period may remain at the site or be asked to return to the site to undergo further safety assessments at the 1-3 business day follow-up time point.

9. Tumor markers include Alpha-fetoprotein, carcinoembryonic antigen, carbohydrate antigen 19.9 (CA19.9) and liver function tests (Alkaline Phosphatase, ALT, AST, Total Bilirubin, Direct Bilirubin). Refer to section **5.1** for more details.
10. Only participants with a positive baseline ¹⁸F-DCFPyL-PET/CT scan (i.e. with the presence of DCFPyL-avid tumor/s) and a biopsy confirming HCC diagnosis will undergo visit 2 for a second ¹⁸F-DCFPyL PET/CT (during routine treatment follow up, typically within 16 weeks).
11. Follow-up will be performed every 3 months (\pm 2 weeks) after the last ¹⁸F-DCFPyL scan (or after therapy for participants with negative baseline ¹⁸F-DCFPyL PET/CT and biopsy confirming HCC) for 2 years, and yearly afterwards for an additional 3 years.
12. If tumor recurrence occurs during the follow-up period, an ¹⁸F-DCFPyL PET/CT, ¹⁸F-FDG PET/CT, CT/MRI and biopsy may be performed any time after recurrence at PI discretion. Biopsy would be performed concurrently with treatment if the latter is performed.
13. Blood collection for tumor markers and EVP analysis may be omitted beyond visit 2 if any issues with scheduling or logistics. The same applies to urine collection for EVP analysis.

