5 CORRELATIVE STUDIES FOR RESEARCH

5.1 BIOSPECIMEN COLLECTION

Table 2. Summary of Collection of Correlative Samples

Test/assay	Quantity (approx)	Type of tube ^a	Collection timepoint	Location of specimen	Sample data system used
Tissue samples					
IHC	4 cores per lesion (18G)	NA	Concurrently with standard of care treatment	Laboratory of Pathology (LP)/COMPASS	Labmatrix
PSMA staining				Blood Processing Core ([name] lab)	
Next Generation Sequencing				CCR Sequencing Facility [name] laboratory Participating sites should process and ship samples to [name] lab per section 5.3 .	
Blood samples					
Alpha-fetoprotein ^b	3.5 mL	1 SST	Within 30 days of each ¹⁸ F-DCFPyL PET/CT imaging	Participating site Clinical Center laboratory or Outside Clinical facility	C3D
Carcinoembryonic antigen ^b					
Carbohydrate antigen 19.9 ^b					
Liver function tests (Alkaline Phosphatase, ALT, AST, Total Bilirubin, Direct Bilirubin) ^b	3.5 mL	1 Green Lithium heparin			

Test/assay	Quantity (approx)	Type of tube ^a	Collection timepoint	Location of specimen	Sample data system used
Germline Mutation Control	3 mL	1 Sodium Citrate tube	Baseline	Laboratory of Pathology/COMPASS	Labmatrix
EVP analysis ^b	3.5 mL	2 SST tubes	Baseline, Study Visit 2 Follow-up Progression	[name] lab	Labmatrix
	10 mL	2 Streck DNA BCT	Baseline Study Visit 2 Follow-up Progression	[name] lab	Labmatrix
	20 mL	2 Streck complete (RNA, EV) BCT	Baseline Study Visit 2 Follow-up Progression	[name] lab	Labmatrix
Urine Sample					
EVP analysis ^b	50mL	Urine cup	Baseline Study Visit 2 Follow-up Progression	[name] lab	Labmatrix

a. Please note that tubes and media may be substituted based on availability with the permission of the PI or laboratory investigator.
 b. May be omitted beyond visit 2 if any issues with scheduling or logistics.

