5.2.2 HCC Blood Biomarker Studies/Tumor Marker Tests

Alpha-fetoprotein, carcinoembryonic antigen, carbohydrate antigen 19.9 (CA19.9) and liver function tests (Alkaline Phosphatase, ALT, AST, Total Bilirubin, Direct Bilirubin) will be performed (may done by an outside facility)

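### Section 12.3.1.8 gives blood maxima of 17 mL per PET visit and 7 mL per follow-up visit, but Table 2 on its lowest reading lists up to 43.5 mL at baseline, 40.5 mL at Visit 2 or progression and 33.5 mL at follow-up

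*Combined protocol and SAP*

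**What the plan says.** In the Combined protocol and SAP, section 12.3.1.8 gives two maxima. For visits with a DCFPyL PET/CT it says "Up to 17 mL of blood maybe collected at each study visit". For follow-up it says "Up to 7 mL of blood may be collected at each follow-up visit".

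Table 2 in section 5.1 lists the research blood:

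- **Tumor markers:** 3.5 mL, one SST tube, collected "Within 30 days of each ¹⁸ F-DCFPyL PET/CT imaging".
- **Liver function tests:** 3.5 mL, one green tube, at the same times.
- **Germline control:** 3 mL, one tube, baseline only.
- **EVP blood:** three rows of 3.5 mL (two SST tubes), 10 mL ("2 Streck DNA BCT") and 20 mL ("2 Streck complete (RNA, EV) BCT"), each at baseline, Visit 2, follow-up and progression.

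The calendar in section 3.3 has a line for "Blood and urine for EVP analysis" marked at the same four points. Its note 13 adds: "Blood collection for tumor markers and EVP analysis may be omitted beyond visit 2", if there are scheduling or logistical problems. Section 5.2.2 says that the marker and liver tests "may done by an outside facility".

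**The concern.** An 'up to' figure should cover everything that the schedule allows to be drawn at that visit. Here one row of Table 2, at 20 mL, is larger than either maximum before any other tube is added.

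These are the only blood volumes that the risk section states, so anyone judging participant burden relies on them. The excess includes baseline and Visit 2, where the option to omit samples does not apply. Staff who took 17 and 7 mL as limits could not fill the Streck tubes as listed, and those tubes are 30 of the 33.5 mL of EVP blood per time point on the row-total reading. Staff who followed Table 2 would exceed what the risk section discloses.

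**Working it through.** **Inputs (mL, from Table 2, section 5.1)**

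| Row | Volume | Tubes | Baseline | Visit 2 / progression | Follow-up |
|---|---|---|---|---|---|
| Tumor markers | 3.5 | 1 | yes | yes | no |
| Liver tests | 3.5 | 1 | yes | yes | no |
| Germline control | 3 | 1 | yes | no | no |
| EVP, SST | 3.5 | 2 | yes | yes | yes |
| EVP, Streck DNA | 10 | 2 | yes | yes | yes |
| EVP, Streck complete | 20 | 2 | yes | yes | yes |

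The total for a visit is the sum of the rows that apply. Table 2 does not say whether a volume is per tube or per row, so three readings were tried.

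**Step 1: can the stated 17 and 7 mL be reproduced?** Not from the full table on any of the three readings. They do come out if both Streck rows are dropped and the EVP SST row is read per tube:

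- Baseline: 3.5 + 3.5 + 3 + 2 × 3.5 = 17
- Follow-up: 2 × 3.5 = 7

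Dropping the Streck rows but reading the SST row as a total gives 13.5 and 3.5, which do not match.

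**Step 2: full table, each volume a row total (lowest reading)**

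- Baseline: 3.5 + 3.5 + 3 + 3.5 + 10 + 20 = 43.5
- Visit 2 or progression: 43.5 − 3 = 40.5
- Follow-up: 3.5 + 10 + 20 = 33.5

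Ratios to the stated maxima: 43.5/17 = 2.56; 40.5/17 = 2.38; 33.5/7 = 4.79.

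**Step 3: the other readings**

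| Reading | Baseline | Visit 2 / progression | Follow-up | Ratios |
|---|---|---|---|---|
| All rows as totals | 43.5 | 40.5 | 33.5 | 2.6, 2.4, 4.8 |
| EVP SST per tube, Streck as totals | 47 | 44 | 37 | 2.8, 2.6, 5.3 |
| All rows per tube | 77 | 74 | 67 | 4.5, 4.4, 9.6 |

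The second line adds 3.5 to the first. The third is 3.5 + 3.5 + 3 + 7 + 20 + 40 = 77 at baseline, 77 − 3 = 74 at Visit 2 or progression, and 7 + 20 + 40 = 67 at follow-up.

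**Step 4: marker and liver tubes drawn elsewhere (row totals)**

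- Baseline: 43.5 − 7 = 36.5, and 36.5/17 = 2.15
- Visit 2: 40.5 − 7 = 33.5, and 33.5/17 = 1.97

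Blood for the CBC and chemistry panel at Visit 2 has no stated volume and is left out of every total.

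**The case against.** Several provisions soften the comparison.

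- **Omission.** EVP and marker blood may be skipped after Visit 2, follow-up is largely remote, and sampling at recurrence is at the investigator's discretion (section 3.1). The follow-up and progression totals are therefore ceilings, not expected draws. That stands, but an optional sample still counts toward an 'up to' figure, and the option does not reach baseline or Visit 2.
- **Splitting the draw.** Marker and liver tubes may be taken elsewhere, and baseline work may be spread over 30 days. Step 4 shows that the first leaves about twice the stated figure. The second could lower a single baseline draw, but the 20 mL row by itself is above 17 mL, and splitting does not explain follow-up.
- **Approximate volumes and tube substitution.** Table 2 allows both and sets no bounds on substitution. It is unlikely that they absorb a gap of this size.
- **Which side is wrong.** The documents do not settle this. Section 3.1.3 of the NIH supplement (the document named Protocol) speaks of serum and urine EVP samples and does not mention Streck tubes, which fits an SST-only count. The tube list could be the part to change. This point stands and bears on the remedy, not on whether the sections conflict.
- **Practical weight.** Section 12.3.1.8 describes risk; Table 2 and the calendar govern collection. No separate volume limit is given. The fair reading is a conflict in disclosed burden, and staff may well simply follow Table 2.

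**Conclusion.** The contradiction holds on every reading tried, and no passage reconciles it. On the lowest reading the listed blood is 2.6 times the stated maximum at baseline, 2.4 times at Visit 2 or progression and 4.8 times at follow-up. Even without the marker and liver tubes, the two PET visits at which sampling is not optional come to about twice the stated 17 mL.

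The result rests on the Table 2 volumes as printed and on taking an 'up to' figure as the most that may be drawn. That the Streck tubes were left out of the count is an inference from the exact match in Step 1; the conflict does not depend on it. No endpoint analysis uses these volumes. The correction should be made because a risk statement and a collection schedule in the same protocol disagree by a wide margin.

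**What to change.** 1. State in Table 2 whether each volume is per tube or per row.
2. Decide whether the tube list or the risk text reflects what is intended. If the tube list stands, recompute the maxima in section 12.3.1.8 separately for baseline, Visit 2 or progression, and follow-up. If the smaller volumes were intended, correct the tube list.
3. Say whether the maxima cover research blood only, since the CBC and chemistry volumes are not given.
4. Check that the consent, which was not available for this review, carries the same figures.

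If the tube list stands, the cost is a text correction in section 12.3.1.8 and one note to Table 2; otherwise it is an edit to Table 2. The consent changes only if its figures no longer match. The analysis plan is untouched.

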12.3.1.9 Risk of Biopsy

All care will be taken to minimize risks that may be incurred by tumor sampling. Procedure-related risks include pain, bleeding, tenderness, scarring, and infection. Complications from biopsies may be life threatening and may include organ damage.

There is a possibility that conscious sedation may be used for the procedure. The common side effects of conscious sedation include drowsiness, delayed reflexes, hypotension, headache, and nausea. These are generally mild and last no more than a few hours.

12.3.1.10 Risk from Urine Collection

There are no known risks associated with urine collection.

12.3.1.11 Known Potential Benefits

There are no direct benefits to the study participant; however, the study results may help the investigators learn more about the effectiveness of ¹⁸F-DGDPyL imaging in identifying sites of HCC and could help confirm treatment success.

12.4 CONSENT PROCESS AND DOCUMENTATION

The informed consent document will be provided as a physical or electronic document to the participant as applicable for review prior to consenting. A designated study investigator will carefully explain the procedures and tests involved in this study, and the associated risks, discomforts and benefits. In order to minimize potential coercion, as much time as is needed to review the document will be given, including an opportunity to discuss it with friends, family

members and/or other advisors, and to ask questions of any designated study investigator. A signed informed consent document will be obtained prior to entry onto the study.

The initial consent process as well as re-consent, when required, may take place in person or remotely (e.g., via telephone or other NIH approved remote platforms used in compliance with local policy, and/including HRPP Policy 303) per discretion of the designated study investigator and with the agreement of the participant. Whether in person or remote, the privacy of the subject will be maintained. Consenting investigators (and participant, when in person) will be located in a private area (e.g., clinic consult room). When consent is conducted remotely, the participant will be informed of the private nature of the discussion and will be encouraged to relocate to a more private setting if needed.

Consent will be documented with required signatures on the physical document (which includes the printout of an electronic document sent to participant) or on the electronic document, with a manual (non-electronic) signature on the electronic document. When required, witness signature will be obtained similarly as described for the investigator and participant.

Please see site specific supplement for electronic signature requirements for each site.

13 REGULATORY AND OPERATIONAL CONSIDERATIONS

13.1 STUDY DISCONTINUATION AND CLOSURE

This study may be temporarily suspended or prematurely terminated if there is sufficient reasonable cause. Written notification, documenting the reason for study suspension or termination, will be provided by the suspending or terminating party to study participants, investigator, funding agency, the Investigational New Drug (IND) sponsor and regulatory authorities. If the study is prematurely terminated or suspended, the Principal Investigator (PI) will promptly inform study participants, the Institutional Review Board (IRB), and sponsor and will provide the reason(s) for the termination or suspension. Study participants will be contacted, as applicable, and be informed of changes to study visit schedule.

Circumstances that may warrant termination or suspension include, but are not limited to:

- Determination of unexpected, significant, or unacceptable risk to participants
- Demonstration of efficacy that would warrant stopping
- Insufficient compliance to protocol requirements
- Data that are not sufficiently complete and/or evaluable
- Determination that the primary endpoint has been met
- Determination of futility

Study may resume once concerns about safety, protocol compliance, and data quality are addressed, and satisfy the sponsor, IRB and as applicable, Food and Drug Administration (FDA).

13.2 QUALITY ASSURANCE AND QUALITY CONTROL

Each clinical site will perform internal quality management of study conduct, data and biological specimen collection, documentation and completion. An individualized quality management plan will be developed to describe a site's quality management.

Quality control (QC) procedures will be implemented beginning with the data entry system and data QC checks that will be run on the database will be generated. Any missing data or data anomalies will be communicated to the site(s) for clarification/resolution.

Following written Standard Operating Procedures (SOPs), the monitors will verify that the clinical trial is conducted and data are generated and biological specimens are collected, documented (recorded), and reported in compliance with the protocol, International Council on Harmonisation Good Clinical Practice (ICH GCP), and applicable regulatory requirements (e.g., Good Laboratory Practices (GLP), Good Manufacturing Practices (GMP)).

The investigational site will provide direct access to all trial related sites, source data/documents, and reports for the purpose of monitoring and auditing by the sponsor, and inspection by local and regulatory authorities.

13.3 CONFLICT OF INTEREST POLICY

The independence of this study from any actual or perceived influence, such as by the pharmaceutical industry, is critical. Therefore, any actual conflict of interest of persons who have a role in the design, conduct, analysis, publication, or any aspect of this trial will be disclosed and managed. Furthermore, persons who have a perceived conflict of interest will be required to have such conflicts managed in a way that is appropriate to their participation in the design and conduct of this trial. The study leadership in conjunction with the NCI has established policies and procedures for all study group members to disclose all conflicts of interest and will establish a mechanism for the management of all reported dualities of interest.

13.4 CONFIDENTIALITY AND PRIVACY

Participant confidentiality and privacy is strictly held in trust by the participating investigators, their staff, and the sponsor(s). This confidentiality is extended to cover testing of biological samples and genetic tests in addition to the clinical information relating to participants.

Therefore, the study protocol, documentation, data, and all other information generated will be held in strict confidence. No information concerning the study or the data will be released to any unauthorized third party without prior written approval of the sponsor.

All research activities will be conducted in as private a setting as possible.

The study monitor, other authorized representatives of the sponsor, representatives of the Institutional Review Board (IRB), and/or regulatory agencies may inspect all documents and records required to be maintained by the investigator, including but not limited to, medical records (office, clinic, or hospital) and pharmacy records for the participants in this study. The clinical study site will permit access to such records.

The study participant's contact information will be securely stored at the/each clinical site for internal use during the study. At the end of the study, all records will continue to be kept in a secure location for as long a period as dictated by the reviewing IRB, Institutional policies, or sponsor requirements.

Study participant research data, which is for purposes of statistical analysis and scientific reporting, will be stored at the NCI CCR. This will not include the participant's contact or identifying information. Rather, individual participants and their research data will be identified by a unique study identification number. The study data entry and study management systems

used by the clinical site(s) and by NCI CCR research staff will be secured and password protected. At the end of the study, all study databases will be archived at the NIH.

To further protect the privacy of study participants, a Certificate of Confidentiality has been issued by the National Institutes of Health (NIH). This certificate protects identifiable research information from forced disclosure. It allows the investigator and others who have access to research records to refuse to disclose identifying information on research participation in any civil, criminal, administrative, legislative, or other proceeding, whether at the federal, state, or local level. By protecting researchers and institutions from being compelled to disclose information that would identify research participants, Certificates of Confidentiality help achieve the research objectives and promote participation in studies by helping assure confidentiality and privacy to participants.

